#### **11.3.8. Malaria Clinical Score**

Malaria clinical score data will be listed for all participants, including the individual scores for each of the 14 signs/symptoms as well as the total score.

The number (and percentage) of participants scoring each symptom (0=absent; 1=mild; 2=moderate; 3=severe) will be tabulated per dose group and per protocol defined timepoint.

The highest score as well as the time(s) to the highest score observed will be tabulated.

#### **11.3.9. Presentation of Safety Results**

The table summary and listings of AEs and lab parameters will be presented for the CSR, and are provided in Appendix, Table B.

## 12. EXPLORATORY PARAMETERS

### Analysis Set: PD Analysis Set

Endpoint: Incidence and level of resistance to MMV367 in parasites determined using *in vitro* methods.

Parasites will be genotyped and *in vitro* drug sensitivity testing will be performed.

Endpoint: Effect of MMV367 on parasite viability in *ex vivo* cultures.

*Ex vivo* growth is a measure of parasite viability. An estimate of the number of viable parasites following MMV367 treatment will be quantified using a limiting dilution assay by counting the number of wells with parasite growth using the following formula [8] :

$$\text{Viable parasites} = X^{n-1},$$

Where n is the number of wells with parasite growth and X is the dilution factor used in the assay. If no wells exhibit parasite growth (i.e. n=0) the number of viable parasites is estimated to be zero. Short term *ex vivo* cultures will be established from blood samples collected pre-MMV367 administration (Day 8), then at several time-points post-MMV367 administration. An estimate of the number of initial parasites will be established using the pre-MMV367 administration samples, which will be used to calculate a normalization factor for post-MMV367 administration samples. Limiting dilution assays will be run for participant samples in triplicate, with the estimate of the number of viable parasites described for each sample as a mean (SD) on the log-scale. Estimates of both the raw number of viable parasites and the normalized number of viable parasites will be presented. Estimates of viable parasites may also be summarized by MMV367 dose per study time-point, with dose comparisons assessed using ANOVA, Kruskal Wallis tests or equivalent, as appropriate. The results of parasite *ex vivo* growth analyses will be supportive to malaria 18S qPCR data in determining the kinetics of parasite clearance following MMV367 dosing (secondary endpoint).

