3 OBJECTIVES AND ENDPOINTS

OBJECTIVES	ENDPOINTS
Primary	
To characterise the PK/PD relationship of MMV367 in healthy participants experimentally infected with blood stage P. falciparum .	The PK/PD relationship between MMV367 blood concentrations and blood stage asexual parasitaemia.
Secondary	
To evaluate the safety and tolerability of single oral doses of MMV367 in healthy participants experimentally infected with blood stage P. falciparum .	The incidence, severity and relationship to MMV367 of adverse events as determined by self-reported symptoms, clinical laboratory analysis, vital signs, physical examinations and ECG assessments.
To evaluate the safety and tolerability associated with blood-stage malaria infection in healthy malaria naïve participants.	The incidence, severity and relationship to the malaria challenge agent of adverse events as determined by self-reported symptoms, clinical laboratory analysis, vital signs, physical examinations and ECG assessments. Additionally, the severity of the induced malaria infection in each participant graded by the malaria clinical score.
To characterise the pharmacokinetics of MMV367 following single oral dose administration in healthy participants experimentally infected with blood stage P. falciparum .	The pharmacokinetics of MMV367 calculated using non-compartmental methods (C_{max} , t_{max} , AUC_{last} , AUC_{inf} , CL/F , Vz/F , λ , $t_{1/2}$).
To characterise the parasite clearance kinetics following single doses of MMV367 in healthy participants experimentally infected with blood-stage P. falciparum .	The parasite clearance kinetics following dosing with MMV367 (parasite reduction ratio over a 48-hour period [PRR_{48}] and corresponding parasite clearance half-life [$PCt_{1/2}$]).
Exploratory	
To investigate potential resistance of P. falciparum to MMV367 in participants experiencing parasite regrowth after MMV367 administration.	Incidence and level of resistance to MMV367 in parasites determined using in vitro methods.
To characterise the effect of MMV367 on P. falciparum parasite viability.	Effect of MMV367 on parasite viability examined by ex vivo cultures.

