8.2.7.12 PARASITE EX VIVO VIABILITY

Determining parasite growth in *ex vivo* cultures is an exploratory objective of this study. *Ex vivo* growth is a measure of parasite viability. While 18S qPCR quantifies all parasites (including those non-viable or dead in circulation), only viable parasites are able to replicate in *ex vivo* culture. Modelling of parasite growth observed *ex vivo* enables the fraction of viable parasites present in blood samples to be determined. The results of parasite *ex vivo* growth analyses will be supportive to malaria 18S qPCR data in determining the kinetics of parasite clearance following MMV367 dosing (secondary endpoint). Short term *ex vivo* cultures will be established from blood samples collected pre-MMV367 administration (Day 8), then at several time-points post-MMV367 administration.

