- Collect blood for parasite *ex vivo* viability at 8, 16, 24, 36 and 48 hours post-MMV367 administration.
- Record AEs and use of concomitant medications.

The following procedures will occur prior to discharge from the clinical trial unit (Day 11AM):

- Perform symptom-directed physical examination if clinically indicated.
- Obtain a 12-lead ECG.
- Obtain malaria clinical score.
- Record vital signs.
- Collect blood samples at 72 hours post-MMV367 administration for:
 - haematology and biochemistry,
 - malaria PCR,

- IMP PK,
- parasite *ex vivo* viability.
- Record AEs and use of concomitant medications.

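### SAP 12 reports a number of viable parasites but not the viable fraction that Protocol 8.2.7.12 describes, so an optional dose comparison of viability could reflect faster clearance.

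*SAP*

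**What the plan says.** The exploratory endpoint in Protocol section 3 reads "Effect of MMV367 on parasite viability examined by" ex vivo cultures. Protocol 8.2.7.12 explains why culture is needed as well as PCR: "18S qPCR quantifies all parasites (including those non-viable or dead in circulation), only viable parasites are able to replicate" in culture. It adds that modelling the growth "enables the fraction of viable parasites present in blood samples to be determined".

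SAP 12 begins: "An estimate of the number of viable parasites following MMV367 treatment will be quantified using a limiting dilution assay". The estimate is X^(n-1), where X is the dilution factor and n the number of wells with growth; it is zero if n = 0. The pre-dose samples give an initial estimate, "which will be used to calculate a normalization factor for post-MMV367 administration samples". On output the SAP says: "Estimates of both the raw number of viable parasites and the normalized number of viable parasites will be presented". It also permits, without requiring, summaries by dose and time point with ANOVA, Kruskal-Wallis or similar comparisons. It describes the results as support for the 18S data on clearance kinetics.

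Neither SAP 12 nor the output list in SAP Appendix Table A divides the viable number by the 18S count at the same post-dose time. SAP 10.3.3 mentions viable counts only in a gametocyte exclusion rule, and the modelling dataset it describes keeps total counts. SAP 13 declares no change to the planned analysis.

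In Protocol 12.1.5, ex vivo samples are drawn pre-dose, "at 8, 16, 24, 36 and 48 hours post-MMV367 administration", and at 72 h; 12.1.6 adds Day 12. Malaria PCR is scheduled at each of these times.

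**The concern.** Viability is a property of the parasites present: what share of them can still replicate. A number of viable parasites combines that share with how many parasites are left. The two move together after an effective dose, because total parasitaemia falls over the same hours in which cultures are taken.

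A factor fixed at pre-dose is the same for all of a participant's post-dose samples. Whatever its form, it cannot remove a decline that happens after dosing. The consequences are limited to two uses of the output: a statement that the parasites remaining at a given time have lost viability, and a comparison of doses on viability. A dose that clears parasites faster would show a lower viable number at each time even if its surviving parasites were no less viable.

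**Working it through.** The documents give no numerical target for this endpoint, so there is no figure to reproduce. The check is how the planned output behaves when viability does not change.

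**Inputs**
- L = predicted log10 PRR48 (Protocol 4.3): 2.9 for 20 mg (95% range 0.26 to 5.8) and 3.6 for 90 mg (1.8 to 6.2).
- Pre-dose parasitaemia: above 5,000/mL for most participants (Protocol 12.1.5). I use 5,000/mL for absolute counts; it cancels in relative ones.
- Assumptions, not in the documents: log-linear decline, and cultures seeded by blood volume.

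**Formulas**
- Total count: T(t) = T(0) × 10^(−L·t/48).
- Viable count: V(t) = v(t) × T(t), with v the viable share.
- Viable count relative to pre-dose: V(t)/V(0) = [v(t)/v(0)] × 10^(−L·t/48). A constant pre-dose factor cancels here.
- Relative viable fraction: [V(t)/T(t)] / [V(0)/T(0)] = v(t)/v(0).

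**Viability unchanged, v(t) = v(0)**

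| Time | 20 mg, viable number vs pre-dose | 90 mg, viable number vs pre-dose | 20 mg / 90 mg = 10^(0.7·t/48) |
|---|---|---|---|
| 8 h | 32.9% | 25.1% | 1.3 |
| 16 h | 10.8% | 6.3% | 1.7 |
| 24 h | 3.5% | 1.6% | 2.2 |
| 36 h | 0.67% | 0.20% | 3.3 |
| 48 h | 0.13% | 0.025% | 5.0 |

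The relative viable fraction is 1.00 in every cell. The 48 h falls are 10^2.9 = 794-fold and 10^3.6 = 3,981-fold.

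**Over the protocol's ranges, 48 h**
- 20 mg: 10^−0.26 = 55% to 10^−5.8 = 0.00016% (1.8-fold to about 630,000-fold).
- 90 mg: 10^−1.8 = 1.6% to 10^−6.2 = 0.00006%.

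**Same output from different states.** A viable number at 0.13% of pre-dose can arise with a 794-fold fall in total count and a relative fraction of 1.00. It can also arise with no fall in total count and a relative fraction of 0.0013. The viable number alone does not distinguish them; the fraction does.

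**If seeding is to a fixed number.** Suppose each culture receives S parasites according to its own 18S count. Then V(t) = v(t) × S, and the normalised count equals v(t)/v(0). The planned output would already be a relative fraction.

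**Where the fraction can be computed.** Predicted totals from 5,000/mL at the medians:

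| | 8 h | 16 h | 24 h | 36 h | 48 h |
|---|---|---|---|---|---|
| 20 mg, per mL | 1,643 | 540 | 177 | 33 | 6.3 |
| 90 mg, per mL | 1,256 | 315 | 79 | 10 | 1.3 |

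The SAP cites 10/mL as the lower limit of quantification for modelling (10.3.3), and 32/mL (quantification) and 111/mL (detection) for sensitivity analyses (11.1.2). At 111/mL, 90 mg drops out at 24 h while 20 mg does not. At 32/mL, both are above the limit to 24 h.

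**The case against.** The strongest reply is that the viable number is the right quantity for the use SAP 12 names. 18S counts dead parasites and culture does not, so the viable number is a separate measurement that can fall faster than 18S. That stands. A reader might infer that the assay's support for the 18S data is circular; the documents do not support this.

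A reader might also infer that the trial cannot separate loss of viability from removal. That goes too far as well. 18S is listed and profiled at matching times, so the information exists, and SAP 2 allows labelled post hoc analyses. What is missing is a pre-specified use of it.

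Nor can one say that ordinary clearance is being mistaken for a drug effect. In Protocol 9.4.2 and SAP 10.4.3 the decline of living parasites is net growth minus a killing or clearance rate due to MMV367, so a fall in the viable number is itself a drug effect. Full viability of every remaining parasite is a test case, not a prediction.

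The seeding basis is unknown, and laboratory processing is deferred to the Laboratory Manual (Protocol 8.2.7). Silence is not evidence of volume seeding, so the sizes are conditional. Finally, the endpoint is exploratory, Protocol 9.4.9 plans no formal statistical analysis of it, the dose comparison in SAP 12 is optional, and Protocol 8.2.7.12 describes what the method enables without defining a reported endpoint. These facts make the point a minor one. They do not reconcile the fraction in the protocol with the number in the SAP.

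**Conclusion.** The point holds as a low-severity improvement. The protocol describes a viable fraction; the SAP specifies only a viable number, with no denominator from the same post-dose time. A pre-dose factor cannot supply one.

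If cultures are seeded by volume, clearance alone would lower the number to 3.5% (20 mg) and 1.6% (90 mg) of pre-dose at 24 h under the median predictions. It would also produce an apparent difference between these doses of 2.2-fold at 24 h and 5.0-fold at 48 h with identical viability. These figures assume log-linear decline, and the protocol's ranges around the medians are very wide. The estimate also moves in steps of X, which the SAP does not state, so a 2-fold difference may not be visible in a single culture. If cultures are seeded to a fixed parasite number, only a statement of that fact is needed.

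The consequence is confined to statements about the viability of remaining parasites and the optional dose comparison. Primary, secondary and safety results are unaffected.

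**What to change.** In SAP 12:

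1. State the seeding basis of the cultures and the formula of the normalising factor.
2. Unless seeding is to a fixed parasite number, add the viable fraction per participant and time: viable count divided by the 18S count at the same time, then divided by the same ratio pre-dose. Show it beside the viable count, which stays. Put both counts on one volume basis; Protocol 8.1.2 reports 18S per 500 µL of packed red cells, while SAP 10.3.1 uses counts per mL.
3. Base statements about viability of remaining parasites, and any dose comparison of viability, on the fraction at times when most participants in every compared dose are evaluable. This is probably 8 to 24 h, or 8 to 16 h if the 111/mL limit is chosen.
4. Name one 18S limit below which the fraction is not evaluable. Do not use the 1 parasite/mL substitution of SAP 11.1.1 as a denominator. State how n = 0 is handled, and report the number evaluable by dose and time.

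The cost is one derived variable from samples already scheduled. The drawback is that evaluability depends on dose and speed of clearance. From 5,000/mL at the medians, 90 mg predicts about 79/mL at 24 h and 1.3/mL at 48 h, so later comparisons would rest on selected participants. That is why the fraction should accompany the count rather than replace it.

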## 13. CHANGES TO THE PLANNED ANALYSIS

There is no change to the planned analysis by the time this SAP was written.

## 14. INTERIM AND FINAL ANALYSIS

This study has no formal interim analyses other than review of safety, tolerability, parasitaemia and PK parameters by the SDRT between cohorts.

## 15. SOFTWARE

SAS® Version 9.4 or higher (SAS Institute, Cary, North Carolina, USA) for Safety, demographic and baseline characteristics, participant disposition, protocol deviations, prior medications and treatment exposure analyses

All PK/PD analyses will be performed in R 4.1.3 and IQRtool package 1.10.0 [IQRtools]. NLME modelling will be performed with Monolix 2019R1 [MLX19] using Stochastic Approximation Expectation Maximization (SAEM) for parameter estimation. For PD modelling where typically the variance of random effects cannot be estimated

from the data, the IQRtools SysFit approach [KAS19] will be used to estimate typical and individual PD parameters.

Data manipulation and data analyses for all pharmacodynamic data will be performed using R (highest version available).

## 17. APPENDIX

**Table A. PD and PK Planned Tables, Listings and Figures**

Title	Analysis Set
PD Listings	
Pharmacodynamic –Parasitemia	PD
Pharmacodynamic –Parasite Life Cycle Stages	PD
PK Listings	
Pharmacokinetic Concentrations	PK
Pharmacokinetic Parameters	PK
PD Tables	
Summary of Malaria Parasitaemia (18S qPCR)	PD

Summary of Malaria Parasite Lifecycle Stage Data (pfs25, pfMGET and SBP-1 qRT-PCR)	PD
PK Tables	
Summary of Pharmacokinetic Concentration	PK
Summary of Pharmacokinetic Parameters	PK
PD Figures	
Individual qPCR 18s-time Profiles	PD
Individual RT-PCR pfs25-time Profiles	PD
Individual RT-PCR pfMGET-time Profiles	PD
Individual RT-PCR SBP-1-time Profiles	PD
PK Figures	
Arithmetic Mean (+SD) Pharmacokinetic Concentration-time Profiles by Dose Group	PK
Individual Pharmacokinetic Concentration-time Profiles	PK

**Table B. Baseline Characteristics and Safety Analysis Tables and Listings**

Title	Analysis Set
Listings	
Participant Disposition	FAS
Dose Group Assignment	FAS
Protocol Deviations	FAS
Analysis Population Assignment	FAS
Demographics	FAS
Medical History	FAS
Pregnancy Test	FAS
Follicle Stimulating Hormone (FSH)	FAS
Viral Screen	FAS
Urine Drug Screening	FAS
Alcohol Breath Test	FAS
Positive SARS-CoV-2	FAS
Prior Medications	
Concomitant Medications	FAS
Inoculum Administration	FAS
IMP Administration	FAS
Rescue Medication Administration	FAS
Inoculum-Emergent Adverse Events	FAS
Treatment-Emergent Adverse Events	IMP
Inoculum related Inoculum-Emergent Adverse Events	FAS
IMP related Treatment-Emergent Adverse Events	IMP
Inoculum Emergent Serious Adverse Events	FAS
Treatment Emergent Serious Adverse Events	IMP
Inoculum-Emergent Adverse Events Leading to Discontinuation	FAS
Treatment-Emergent Adverse Events Leading to Discontinuation	IMP
Inoculum-Emergent Adverse Events of Special Interest	FAS
Treatment-Emergent Adverse Events of Special Interest	IMP

Deaths	FAS
Individual Haematology Results	FAS
Individual Biochemistry Results	FAS
Coagulation Screening	FAS
Individual Urinalysis Results (dipstick)	FAS
Individual Urine Microscopy Results	FAS
Individual Vital Signs Results	FAS
Individual ECG Parameters Results	FAS
Physical Examination	FAS
Malaria Clinical Score Results	FAS
Tables	
Analysis Populations	FAS
Participant Disposition	FAS
Demographics and Baseline Characteristics	FAS
Summary of Prior Medications	FAS
Protocol Deviations	FAS
Overall Summary of Inoculum Emergent Adverse Events	FAS
Overall Summary of Treatment Emergent Adverse Events	IMP
Summary of Inoculum Emergent Adverse Events by MedDRA System Organ Class and Preferred Term (All Causalities)	FAS
Summary of Treatment Emergent Adverse Events by MedDRA System Organ Class and Preferred Term (All Causalities)	IMP
Summary of Inoculum Emergent Adverse Events by Maximum Severity (All Causalities)	FAS
Summary of Treatment Emergent Adverse Events by Maximum Severity (All Causalities)	IMP
Summary of Inoculum related Treatment Emergent Adverse Events by MedDRA System Organ Class, Preferred Term	FAS
Summary of IMP Related Treatment Emergent Adverse Events by MedDRA System Organ Class, Preferred Term	IMP
Summary of Inoculum Related IAEs by System Organ Class, Preferred Term and Maximum Severity	FAS
Summary of IMP Related TEAEs by System Organ Class, Preferred Term and Maximum Severity	IMP
Inoculum Emergent Serious Adverse Events by MedDRA System Organ Class and Preferred Term (All Causalities)	FAS
Treatment Emergent Serious Adverse Events by MedDRA System Organ Class and Preferred Term (All Causalities)	IMP
Overall Summary of Inoculum Emergent Adverse Events of Special Interest (AESI)	FAS
Overall Summary of Treatment Emergent Adverse Events of Special Interest (AESI)	IMP
Inoculum Emergent Adverse Events of Special Interest (AESI) by MedDRA System Organ Class and Preferred Term (All Causalities)	FAS
Treatment Emergent Adverse Events of Special Interest (AESI) by MedDRA System Organ Class and Preferred Term (All Causalities)	IMP
Inoculum Emergent Adverse Events Leading to Study Discontinuation by MedDRA System Organ Class and Preferred Term (All Causalities)	FAS
Treatment Emergent Adverse Events Leading to Study Discontinuation by MedDRA System Organ Class and Preferred Term (All Causalities)	IMP
Summary of Concomitant Medications (FAS)	FAS
Summary of Concomitant Medications (IMP)	IMP
Haematology (Summary and Change from IMP Baseline)	FAS
Haematology (Categorical)	FAS
Biochemistry (Summary and Change from IMP Baseline)	FAS
Biochemistry (Categorical)	FAS
Urinalysis (Continuous) Results and Change from Baseline	FAS
Urinalysis (Categorical) Results	FAS

Vital Signs Results and Change from IMP Baseline	FAS
Abnormal Vital Signs Results	FAS
ECG Results and Change from IMP Baseline	FAS
ECG QTc Categorical Analyses	FAS
ECG Clinical Assessment	FAS
Malaria Clinical Score Summary by Question	FAS
Summary Peak Total Malaria Clinical Score and Time to Peak Total Malaria Clinical Score	FAS

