8.3.6 ADVERSE EVENT REPORTING

It is the Investigator's responsibility to document and report all AEs occurring in the clinical trial whether spontaneously reported by the participant, observed by the Investigator (either directly or by laboratory or other assessments), or elicited by general questioning. The period of observation for collection of AEs extends from the time of inoculation with the malaria challenge agent to EOS. These AEs must be recorded on specific AE pages of the eCRF. Events reported prior to this will be recorded as medical history, unless the symptoms worsen during the trial.

The following information should be recorded for all AEs:

- Description
- Dates and times of onset and resolution
- Seriousness (SAE or not)
- AESI (yes/no)
- Severity
 - If severity of an AE changes, only one AE will be reported, with the highest severity recorded in the eCRF and listings and tables. In the clinical file (source data), the description of the AE will report the various severities observed over time.
 - If the AE resolves and then reoccurs, then two AEs will be reported.
- Action taken in response to the AE (including treatment given).
- Outcome.
- Relationship to the trial treatments or procedures (causality assessment), including the IMP, malaria challenge agent, definitive antimalarial medications, or any other treatment or procedure conducted during the trial.

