#### 3.5.2 Secondary Endpoint (s)

##### 3.5.2.1 Safety Parameters

- The incidence, severity and relationship to MMV367 of adverse events as determined by self-reported symptoms, clinical laboratory analysis, vital signs, physical examinations and ECG assessments.
- The incidence, severity and relationship to the malaria challenge agent of adverse events as determined by self-reported symptoms, clinical laboratory analysis, vital signs, physical examinations and ECG assessments. Additionally, the severity of the induced malaria infection in each participant graded by the malaria clinical score.

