#### **11.3.1. Adverse Events**

AEs will be reported according to the volunteer infection studies (VIS) plausible windows and reporting rules:

---

- Inoculum-emergent AEs (IEAEs)= AEs beginning any time from inoculation with the challenge agent until the end of study.
- Treatment-emergent AEs (TEAEs)= AEs beginning any time from administration of the IMP until the end of study.

Adverse Events of Special Interest (AESIs) may be serious or non-serious and are defined by the Sponsor as being of specific scientific and/or medical concern to the Sponsor's product or program. Evaluation on AESI will be based on both Safety Set and FAS depending on if it is treatment emergent or inoculum emergent adverse events.

Any abnormalities listed below should be reported as an AESI.

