#### 11.3.1.2.2. Tables

The number of events, as well as the number and percentage of participants experiencing an AE, will be summarised by, dose group and overall as follows:

Overall summary of IEAEs (FA set)  
Overall summary of TEAEs (IMP set)

Summary of IEAEs by System Organ Class and Preferred Term - All Causalities (FA set)  
Summary of TEAEs by System Organ Class and Preferred Term - All Causalities (IMP set)

Summary of IEAEs by System Organ Class, Preferred Term and Maximum Severity - All Causalities (FA set)

Summary of TEAEs by System Organ Class, Preferred Term and Maximum Severity - All Causalities (IMP set)

Summary of Malaria-Related IEAEs by System Organ Class and Preferred Term (FA set)  
Summary of IMP-Related TEAEs by System Organ Class and Preferred Term (IMP set)

Summary of Malaria-Related IEAEs by System Organ Class, Preferred Term and Maximum Severity (FA set)

Summary of IMP-Related TEAEs by System Organ Class, Preferred Term and Maximum Severity (IMP set)

Summary of IE SAEs by System Organ Class and Preferred Term - All Causalities (FA set)  
Summary of TE SAEs by System Organ Class and Preferred Term - All Causalities (IMP set)

Overall Summary of IE AESIs (FA set)  
Overall Summary of TE AESIs (IMP set)

Summary of IE AESIs by System Organ Class and Preferred Term - All Causalities (FA set)  
Summary of TE AESIs by System Organ Class and Preferred Term - All Causalities (IMP set)

Summary of IEAEs Leading to Study Discontinuation by System Organ Class and Preferred Term - All Causalities (FA set)

Summary of TEAEs Leading to Study Discontinuation by System Organ Class and Preferred Term - All Causalities (IMP set)

For the summary tables, participants who experience the same AE (in terms of the MedDRA preferred term) more than once will only be counted once.

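### One line of SAP Appendix Table B puts the malaria-related AE table by SOC and PT on the treatment-emergent window, contradicting SAP 11.3.1.2.2

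*SAP*

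**What the plan says.** SAP 11.3.1 defines two classes of adverse event by date of onset. Inoculum-emergent events (IEAEs) are "AEs beginning any time from inoculation with the challenge agent until the end of study". Treatment-emergent events (TEAEs) are "AEs beginning any time from administration of the IMP until the end of study".

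SAP 11.3.1.2.2 lists the AE tables. The malaria-related table by system organ class (SOC) and preferred term (PT) appears there as "Summary of Malaria-Related IEAEs by System Organ Class and Preferred Term (FA set".

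SAP 11.3.9 points to Appendix Table B for the AE tables and listings that go into the CSR. In Table B the corresponding line reads "Summary of Inoculum related Treatment Emergent Adverse Events by MedDRA System Organ Class, Preferred Term", with the FAS as its analysis set. Two neighbouring Table B items deal with the same events:

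- the listing "Inoculum related Inoculum-Emergent Adverse Events" (FAS);
- the table "Summary of Inoculum Related IAEs by System Organ Class, Preferred Term and Maximum Severity" (FAS).

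The abbreviation in the second title is not defined anywhere in the SAP.

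The endpoint served is in SAP 3.5.2.1: "The incidence, severity and relationship to the malaria challenge agent of adverse events". Protocol 8.3.6 fixes the collection period: "The period of observation for collection of AEs extends from the time of inoculation with the malaria challenge agent to EOS".

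**The concern.** The same table is specified twice with different event windows, and the SAP does not say which section prevails. Table B is the output list, so a programmer working from it could apply the TEAE flag and produce a table that does not match SAP 11.3.1.2.2.

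The table reports incidence by event type for a stated secondary endpoint on the safety of the induced infection. Protocol 7.1 accepts that some participants may have mild to moderate malaria signs and symptoms before the Day 8 dose. Those events belong in a summary of malaria-related events, and the TEAE window would exclude them. The table could then show fewer participants with an event than the maximum-severity table listed close by.

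**Working it through.** The plan states no figure on this point, so the check is a comparison of the definitions and titles.

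**Step 1. The two windows** (SAP 11.3.1; study days from SAP 3.1)

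- IEAE: onset from Day 0 to end of study (Day 27).
- TEAE: onset from MMV367 dosing on Day 8 to end of study (Day 27).
- Difference: onset after inoculation and before dosing, about 8 days.

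**Step 2. The malaria-related outputs side by side**

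| Output | Place in SAP | Window in title | Set |
|---|---|---|---|
| SOC/PT table | 11.3.1.2.2 | IEAE | FAS |
| SOC/PT table | Table B | **TEAE** | FAS |
| SOC/PT by maximum severity | 11.3.1.2.2 | IEAE | FAS |
| SOC/PT by maximum severity | Table B | IAE (undefined) | FAS |
| Listing | Table B | IEAE | FAS |

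Only the second row conflicts outright. Table B has no other malaria-related SOC/PT table, so this line is the counterpart of the one in 11.3.1.2.2 and not an additional output.

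**Step 3. What a literal build would exclude**

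Both definitions turn on when an event begins. A malaria-related event starting before dosing is an IEAE but not a TEAE, even if it is still present after dosing. Under Protocol 8.3.6 an event whose severity changes stays a single AE, so a pre-dose headache that worsens after dosing would also be excluded. An event that resolves and recurs is recorded as two AEs, so a recurrence after dosing would be counted.

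**Step 4. The denominator**

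The FAS is everyone inoculated (SAP 5.1.1). Protocol 7.1 provides for participants who are inoculated and then given definitive treatment instead of MMV367. Such a participant counts in the FAS and cannot have a TEAE. Dose group is assigned on Day 8 immediately before dosing (SAP 3.7), so the effect would fall mainly on the overall column.

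**Step 5. Size per participant**

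If the FAS holds 18 participants, each participant lost from a PT row moves the overall incidence by 1/18 = 5.6 percentage points. A participant is lost from a row only if all of their related events under that PT began before dosing. The documents do not say how many participants that would be.

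**The case against.** The strongest reply is that the SAP itself shows what was meant. Every other AE table titled treatment-emergent in Table B is on the IMP set, while this one is on the FAS, as are all the inoculum-emergent tables. Table B alternates an inoculum line with a treatment line, and this entry stands in the inoculum position, directly above its IMP-related counterpart. The body text and the Table B listing both give the inoculum window. All of this stands. It makes a labelling slip much more likely than a deliberate change of analysis, and the FAS assignment is better read as evidence of intent than as a second error.

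It is also fair to say that little would be lost from the report. Pre-dose malaria-related events remain in the inoculum-related listing and in the all-causality IEAE tables. If IAEs means IEAEs, they remain in the maximum-severity table too. That table already carries SOC and PT and counts each participant once per PT, so adding across its severity grades recovers participant incidence by PT. This stands, subject to that reading of IAEs.

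Three stronger readings are tempting, and the documents support none of them:

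- *Pre-dose malaria events would vanish from the report.* The exclusion applies to one summary table.
- *About 30% of malaria-related events would be lost.* The pre-dose period is 8/27 = 29.6% of the post-inoculation calendar, but days are not events. Protocol 12.1.4 expects no symptoms on Days 1 to 3, and Protocol 2.2.1 expects absent or mostly mild symptoms up to Day 8. No document gives the share of events beginning before dosing.
- *The pre-dose days are the only period in which malaria effects can be seen apart from the drug.* Protocol 4.2 gives a half-life of about 17 hours, and Protocol 4.3 predicts a return to pre-dose parasitaemia at a median of 7 days after 20 mg. That is 7 × 24 / 17 = 9.9 half-lives, so malaria effects could recur with little drug present.

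What survives the reply is that the title is wrong as written, in the list that defines the CSR outputs.

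**Conclusion.** The contradiction is real and minor. One Table B title conflicts with SAP 11.3.1.2.2. Followed literally, it would produce an incomplete SOC/PT table for a secondary safety endpoint, omitting malaria-related events with onset between inoculation and dosing. It would also retain any undosed participant in the denominator with no possible event.

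The number of events affected cannot be derived from the documents, and no percentage should be attached to it. The primary analysis is not touched, and pre-dose events are still reported elsewhere.

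The conclusion rests on two things: the onset-based definitions in SAP 11.3.1, and the Table B line being the counterpart of the 11.3.1.2.2 table. The statement that the maximum-severity table still carries pre-dose events also assumes that IAEs is a misprint for IEAEs. That is likely, because 11.3.1.2.2 gives that table on IEAEs, but Table B does not say so.

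**What to change.** In Appendix Table B:

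1. Retitle the line *Summary of Inoculum Related Inoculum-Emergent Adverse Events by SOC and PT*, keeping the FAS, so that it matches SAP 11.3.1.2.2.
2. In the companion maximum-severity title, replace IAEs with IEAEs.

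The cost is two lines of text, with no new data, derivation or analysis. The change should be made before database lock and carried into the table shells and programming specifications.
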